**Screening/Introductory Visit (Day -28 to -1)**

- Review medical history to determine eligibility based on inclusion/exclusion criteria.
- Review medications history to determine eligibility based on inclusion/exclusion criteria.
- Obtain informed consent of potential participant verified by signature on written informed consent or electronic informed consent.
- Obtain medical/medications history and demographic information.
- Schedule baseline visit for participants who are have been screened for eligibility and interested in participating and/or learning more about the study.
- Provide participants with instructions needed to prepare for the first study visit.

**Enrollment/Baseline Visit (Visit 1, Day 0)**

- Obtain informed consent of potential participant verified by signature on written informed consent or electronic consent.
- Verify inclusion/exclusion criteria.
- Subjects will complete the questionnaire packet for baseline assessments which will include BPI, PROMIS sleep disturbance, PROMIS fatigue, PHQ-2, and GAD-2. This will be done either in-person, over the phone or electronically via REDCap link sent to subject.

**6.1.2 Intermediate Visits****Study Visit 2 (Visit 2, Day 1, POD 0)**

- Perform randomization.
- Administer the study intervention, ketamine single dose or placebo. Administration of normal saline placebo is standard of care.
- BPI pain severity subscale, opioid use, and side effects (psycho-behavioral questionnaire) will be assessed in person after infusion.
- Record adverse events as reported by participant or observed by investigator and study team.

**Study Visit 3 (Visit 3, Day 2, POD 1+1)**

- Subjects will complete a questionnaire packet containing, BPI, PROMIS fatigue. Side effects (psycho-behavioral questionnaire) will be assessed.
- Assessment of opioid use.
- Participant will be asked to which treatment arm she believes she is assigned.
- If participant is still in the hospital, study staff may administer questionnaires in person or electronically via REDCap.
- If the participant has already been released from the hospital, a research team member will either send the subject an electronic REDCap link to the questionnaires or call the subject to answer the questionnaires on the phone.
- Record adverse events as reported by participant or observed by investigator and study team.

**Study visit 4 (Visit 4, Day 3, POD2+2)**

- BPI, PROMIS fatigue, QoR-15 will be assessed
- Assessment of opioid use.
- Record adverse events as reported by participant or observed by investigator and study team.
- If participant is still in the hospital, study staff may administer questionnaires in person or electronically via REDCap.
- If the participant has already been released from the hospital, a research team member will either send the subject an electronic REDCap link to the questionnaires or call the subject to answer the questionnaires on the phone.

**6.1.3 Final Study Visit****Study Visit 5 (Visit 5, Day 8, POD 7+2)**

- Subjects will complete a questionnaire packet containing BPI, PROMIS fatigue, QoR-15, BCPQ, PHQ-2, GAD-2, and PROMIS sleep disturbance.

CONFIDENTIAL

This material is the property of the NYU School of Medicine and Langone Medical Center. Do not disclose or use except as authorized in writing by the study sponsor

- Assessment of opioid use.
- Record adverse events as reported by participant or observed by investigator and study team.
- If participant is still in the hospital, study staff may administer questionnaires in person or electronically via REDCap.
- If the participant has already been released from the hospital, a research team member will either send the subject an electronic REDCap link to the questionnaires or call the subject to answer the questionnaires on the phone.

#### **6.1.4 Withdrawal/Early Termination Visit/Lost to Follow-up**

Participants are free to withdraw from participation in the study at any time upon request. However, participants should be counseled that they may request stopping the interventional drug but continue to be in the study. They also will be told that follow-up for adverse events is recommended for safety.

Lost to follow-up is defined by the inability to reach a participant after a minimum of two phone calls. All attempts should be documented in the subject's medical records. If it is determined that the subject has died, the site will use permissible local methods to obtain the date and cause of death.

#### **6.1.5 Unscheduled Visit**

Unscheduled visits will be documented in the subjects' record.

### **6.2 Concomitant Medications, Treatments, and Procedures**

All concomitant prescription medications taken during study participation will be recorded on the case report forms (CRFs). For this protocol, a prescription medication is defined as a medication that can be prescribed only by a properly authorized/licensed clinician. Medications to be reported in the CRF are concomitant prescription medications, over-the-counter medications and non-prescription medications.

### **6.3 Rescue Medications, Treatments, and Procedures**

Cardiovascular side effects may be treated based on PACU clinician's decisions. If such side effects persist despite treatment, study drug may be halted.

Psychomimetic side effects will be monitored by study and PACU physicians. Such side effects may be treated with reassurance. If participants continue to complain of anxiety or dysphoria or are agitated, pharmacologic agents (such as benzodiazepines) may be administered based on clinical judgement of PACU clinicians. Benzodiazepine administration will be at discretion of PACU clinician; midazolam in titrated doses of 0.5-1 mg could be considered. If psychomimetic side effects are felt to be severe, with severe hallucinations, delusions, or agitation, study drug will be discontinued.

## **7 Assessment of Safety**

### **7.1 Definition of Adverse Events (AE)**

An **adverse event** (AE) is any symptom, sign, illness or experience that develops or worsens in severity during the course of the study. Intercurrent illnesses or injuries should be regarded as adverse events. Abnormal results of diagnostic procedures are considered to be adverse events if the abnormality:

- results in study withdrawal
- is associated with a serious adverse event
- is associated with clinical signs or symptoms
- leads to additional treatment or to further diagnostic tests
- is considered by the investigator to be of clinical significance

### **7.2 Definition of Serious Adverse Events (SAE)**

#### **Serious Adverse Event**

Adverse events are classified as serious or non-serious. A **serious adverse event** is any AE that is:

- fatal

CONFIDENTIAL

This material is the property of the NYU School of Medicine and Langone Medical Center. Do not disclose or use except as authorized in writing by the study sponsor

- life-threatening
- requires or prolongs hospital stay
- results in persistent or significant disability or incapacity
- a congenital anomaly or birth defect
- an important medical event

Important medical events are those that may not be immediately life threatening, but are clearly of major clinical significance. They may jeopardize the subject, and may require intervention to prevent one of the other serious outcomes noted above. For example, drug overdose or abuse, a seizure that did not result in in-patient hospitalization, or intensive treatment of bronchospasm in an emergency department would typically be considered serious.

All adverse events that do not meet any of the criteria for serious should be regarded as ***non-serious adverse events***.

### **7.3 Definition of Unanticipated Problems (UP)**

#### **Unanticipated Problems Involving Risk to Subjects or Others**

Any incident, experience, or outcome that meets all of the following criteria:

- Unexpected in nature, severity, or frequency (i.e. not described in study-related documents such as the IRB-approved protocol or consent form, the investigators brochure, etc)
- Related or possibly related to participation in the research (i.e. possibly related means there is a reasonable possibility that the incident experience, or outcome may have been caused by the procedures involved in the research)
- Suggests that the research places subjects or others at greater risk of harm (including physical, psychological, economic, or social harm).

### **7.4 Classification of an Adverse Event**

#### **7.4.1 Severity of Event**

For AEs not included in the protocol defined grading system, the following guidelines will be used to describe severity.

- **Mild** – Events require minimal or no treatment and do not interfere with the participant's daily activities.
- **Moderate** – Events result in a low level of inconvenience or concern with the therapeutic measures. Moderate events may cause some interference with functioning.
- **Severe** – Events interrupt a participant's usual daily activity and may require systemic drug therapy or other treatment. Severe events are usually potentially life-threatening or incapacitating.

#### **7.4.2 Relationship to Study Agent**

*The clinician's assessment of an AE's relationship to study drug is part of the documentation process, but it is not a factor in determining what is or is not reported in the study. If there is any doubt as to whether a clinical observation is an AE, the event should be reported. All AEs must have their relationship to study agent assessed. In a clinical trial, the study product must always be suspect. To help assess, the following guidelines are used.*

*For all collected AEs, the clinician who examines and evaluates the participant will determine the AE's causality based on temporal relationship and his/her clinical judgment. The degree of certainty about causality will be graded using the categories below.*

- **Definitely Related** – *There is clear evidence to suggest a causal relationship, and other possible contributing factors can be ruled out. The clinical event, including an abnormal laboratory test result, occurs in a plausible time relationship to drug administration and cannot be explained by concurrent disease or other drugs or chemicals. The response to withdrawal of the drug (dechallenge) should*

CONFIDENTIAL

This material is the property of the NYU School of Medicine and Langone Medical Center. Do not disclose or use except as authorized in writing by the study sponsor

*be clinically plausible. The event must be pharmacologically or phenomenologically definitive, with use of a satisfactory rechallenge procedure if necessary.*

- **Probably Related** – *There is evidence to suggest a causal relationship, and the influence of other factors is unlikely. The clinical event, including an abnormal laboratory test result, occurs within a reasonable time after administration of the drug, is unlikely to be attributed to concurrent disease or other drugs or chemicals, and follows a clinically reasonable response on withdrawal (dechallenge). Rechallenge information is not required to fulfill this definition.*
- **Possibly Related** – *There is some evidence to suggest a causal relationship (e.g., the event occurred within a reasonable time after administration of the trial medication). However, other factors may have contributed to the event (e.g., the participant's clinical condition, other concomitant events). Although an AE may rate only as "possibly related" soon after discovery, it can be flagged as requiring more information and later be upgraded to "probably related" or "definitely related," as appropriate.*
- **Unlikely to be related** – *A clinical event, including an abnormal laboratory test result, whose temporal relationship to drug administration makes a causal relationship improbable (e.g., the event did not occur within a reasonable time after administration of the trial medication) and in which other drugs or chemicals or underlying disease provides plausible explanations (e.g., the participant's clinical condition, other concomitant treatments).*
- **Not Related** – *The AE is completely independent of study drug administration, and/or evidence exists that the event is definitely related to another etiology. There must be an alternative, definitive etiology documented by the clinician.*

#### **7.4.3 Expectedness**

The principal investigator will be responsible for determining whether an AE is expected or unexpected. An AE will be considered unexpected if the nature, severity, or frequency of the event is not consistent with the risk information previously described for the study agent.

#### **7.5 Time Period and Frequency for Event Assessment and Follow-Up**

The occurrence of an AE or SAE may come to the attention of study personnel during study visits and interviews of a study participant presenting for medical care, or upon review by a study monitor. All AEs including local and systemic reactions not meeting the criteria for SAEs will be captured on the appropriate CRF. Information to be collected includes event description, time of onset, clinician's assessment of severity, relationship to study product (assessed only by those with the training and authority to make a diagnosis), and time of resolution/stabilization of the event. All AEs occurring while on study must be documented appropriately regardless of relationship. All AEs will be followed to adequate resolution.

Any medical condition that is present at the time that the participant is screened will be considered as baseline and not reported as an AE. However, if the study participant's condition deteriorates at any time during the study, it will be recorded as an AE. UPs will be recorded in the data collection system throughout the study.

Changes in the severity of an AE will be documented to allow an assessment of the duration of the event at each level of severity to be performed. AEs characterized as intermittent require documentation of onset and duration of each episode.

The PI will record all reportable events with start dates occurring any time after informed consent is obtained until 7 (for non-serious AEs) or 30 days (for SAEs) after the last day of study participation. At each study visit, the investigator will inquire about the occurrence of AE/SAEs since the last visit. Events will be followed for outcome information until resolution or stabilization.

All unresolved adverse events should be followed by the investigator until the events are resolved, the subject is lost to follow-up, or the adverse event is otherwise explained. At the last scheduled visit, the investigator should instruct each subject to report any subsequent event(s) that the subject, or the subject's personal physician, believes might reasonably be related to participation in this study. The investigator

CONFIDENTIAL

This material is the property of the NYU School of Medicine and Langone Medical Center. Do not disclose or use except as authorized in writing by the study sponsor

should notify the study sponsor of any death or adverse event occurring at any time after a subject has discontinued or terminated study participation that may reasonably be related to this study. The sponsor should also be notified if the investigator should become aware of the development of cancer or of a congenital anomaly in a subsequently conceived offspring of a subject that has participated in this study.

## **7.6 Reporting Procedures**

### **7.6.1 Adverse Event Reporting**

#### **Adverse Event Reporting Period**

The PI will record all reportable events with start dates occurring any time after informed consent is obtained until 7 (for non-serious AEs) or 30 days (for SAEs) after the last day of study participation.

At each contact with the subject, the investigator must seek information on adverse events by specific questioning and, as appropriate, by examination. Information on all adverse events should be recorded immediately in the source document, and also in the appropriate adverse event module of the case report form (CRF). All clearly related signs and symptoms should be recorded in the source document, though should be grouped under one diagnosis.

All adverse events occurring during the study period must be recorded. The clinical course of each event should be followed until resolution, stabilization, or until it has been determined that the study treatment or participation is not the cause. Serious adverse events that are still ongoing at the end of the study period must be followed up to determine the final outcome. Any serious adverse event that occurs after the study period and is considered to be definitely and probably related to the study treatment or study participation should be recorded and reported immediately.

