**4.5 Duration of Study Participation**

For the participation in the study, the study will continue for 7 days or 1 week after surgery. There are 5 visits in total, each visit lasting less than 1 hour.

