## 19 Schedule of Events

STUDY ASSESSMENTS & PROCEDURES	Screening (Day -28 to -1)	Baseline/Enrollment (Visit 1, Day 0)	(Visit 2, Day 1, POD 0)	(Visit 3, Day 2, POD 1+1)	(Visit 4, Day 3, POD 2+2)	(Visit 5, Day 8, POD 7+2)
Informed Consent	X	X				
Review and verify of Inclusion/Exclusion Criteria	X	X				
Demographics 	X					
Medical history and medication history	X					
Randomization and administer study intervention ketamine single-dose infusion or placebo			X			
Participants will be asked which treatment arm she believes she has been assigned				X		
Brief Pain Inventory (BPI)		X	X 	X	X	X
PROMIS sleep disturbance		X				X
PROMIS fatigue		X		X	X	X
Breast cancer pain questionnaire (BCPQ)						X
Opioid use and dosage assessment (medical records) and subject reports			X	X	X	X
Assessment of Adverse Events			X	X	X	X
Quality of Recovery (QoR-15)					X	X
Patient Health Questionnaire-2 (PHQ-2)		X				X
Generalized Anxiety Disorder-2 (GAD-2)		X				X
Side Effects (Psycho-Behavioral Questionnaire)			X	X		

Demographics should be collected, includes: age/ date of birth, race, MRN, gender, ethnicity, participant enrollment location, zip code, and disease site.

Only the pain severity subscale.

CONFIDENTIAL

This material is the property of the NYU School of Medicine and Langone Medical Center. Do not disclose or use except as authorized in writing by the study sponsor

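### The 7-day and 30-day adverse-event windows after the last study day have no scheduled follow-up, and participants are asked to report only later events believed related to participation

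*Combined protocol and SAP*

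**What the plan says.** **Window.** Section 7.6.1 sets the recording period for reportable events as "any time after informed consent is obtained until 7 (for non-serious AEs) or 30 days (for SAEs) after the last day of study participation". Section 7.5 repeats it. Section 7.5 also requires AEs arising on study to be documented whatever their relationship, and Section 7.4.2 says that the causality judgment does not decide what is reported.

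**Scheduled collection.** Section 4.5 says that "the study will continue for 7 days or 1 week after surgery". The item "Record adverse events as reported by participant or observed by investigator and study team" first appears in the list for Visit 2 (POD 0) and last in the list for Visit 5 (POD 7+2). In Section 19 the row "Assessment of Adverse Events" is marked at Visits 2, 3, 4 and 5, and no column follows.

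**After Visit 5.** Under Section 7.5, the participant is told at the last visit to report later events that she or her own physician "believes might reasonably be related to participation in this study". The same section has the investigator tell the sponsor of deaths or AEs after participation ends if they may be related to the study. Section 7.6.1 asks for serious events after the study period to be recorded and reported if judged definitely or probably related. The term study period is not defined.

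**Starting point.** Section 7.5 states: "Any medical condition that is present at the time that the participant is screened will be considered as baseline and not reported as an AE". It requires an inquiry at each study visit covering the time since the previous one, and Section 7.6.1 requires questioning at each contact.

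**The concern.** A recording window is only as good as the means of learning what happened in it. Here the window extends 7 or 30 days past the last contact, and no step in the plan finds out what happened in that time. The one instruction participants are given is narrower than the window, because it depends on their own or their physician's belief about cause.

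Participants have a mastectomy with immediate reconstruction (Section 4.1), and an admission to hospital is a serious event under Section 7.2. A woman readmitted on POD 20 who puts it down to surgery has followed her instructions if she says nothing, yet the event lies inside the stated SAE window. An SAE count described by that window would imply follow-up that was not scheduled. As an inference only, belief-filtered reporting could also differ between arms if the psychological effects listed in Section 1.3 let participants guess their allocation.

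There is a smaller point at the front end. Because baseline is the condition at screening, anesthetic and surgical events before the infusion count as on-study AEs. Sections 10 and 10.1 describe no AE analysis that would separate them from events after it.

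**Working it through.** The documents give no calculated figure to reproduce, so the check is calendar arithmetic plus a comparison of sections.

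**Inputs**
- Visit 5 is on POD 7, or POD 9 at the latest (Sections 6.1.3 and 19, read as 7 plus up to 2 days).
- The window ends 7 days (non-serious) or 30 days (serious) after the last study day (Sections 7.5 and 7.6.1).
- Assumption: the last study day is the day of Visit 5.

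**Formulas.** With Visit 5 on POD v, scheduled assessment spans POD 0 to v, which is v + 1 days. The window from POD 0 has v + 1 + t days, where t is 7 or 30. The share with no scheduled contact is t / (v + 1 + t).

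| | Visit 5 on POD 7 | Visit 5 on POD 9 |
|---|---|---|
| Days POD 0 to Visit 5 | 8 | 10 |
| Non-serious window ends | POD 14 | POD 16 |
| Non-serious share uncovered | 7/15 = 47% | 7/17 = 41% |
| SAE window ends | POD 37 | POD 39 |
| SAE share uncovered | 30/38 = 79% | 30/40 = 75% |

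**Sensitivity to the denominator.** The uncovered days are fixed at 7 and 30; the share depends on where counting starts. The documents give three consent lead times: Day -28 (Section 6.1.1), six weeks (Protocol Summary) and two months (Section 4.3, taken as about 61 days). These add 29, 42 and 61 days before Visit 2. With Visit 5 on POD 7, the uncovered SAE share of the whole window is then 30/67 = 45%, 30/80 = 38% and 30/99 = 30%. POD 0 is the relevant start for events that could follow the infusion.

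**Ways an event in the tail can become known**
- Participant report: limited to belief in relatedness to participation (7.5).
- The participant seeking medical care, or a monitor's review (7.5): not limited by relatedness, but not planned for each participant. Section 12 describes monitors checking CRFs and source data.
- The 24-hour and 72-hour SAE deadlines (7.6.2): these cover related and unrelated deaths and life-threatening events, and other SAEs, but they run from when the site becomes aware.
- Follow-up of unresolved events (7.5, 7.6.1): applies to events already known.

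None of these actively seeks new events from every participant after Visit 5.

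**The case against.** The strongest reply has three parts.

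First, the window sentence speaks of reportable events, a term not defined beside it. The regardless-of-relationship sentence in Section 7.5 is separate and concerns AEs on study. So no single sentence promises that every event of any cause is captured to day 30. That is fair as to wording. However, Sections 7.4.2 and 7.6.2 do not make relatedness a condition for recording an SAE, and on any reading nothing is scheduled after Visit 5.

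Second, the relatedness limit in Section 7.6.1 may apply only beyond the 30-day window, since study period is undefined. This also stands: a reader might infer that 7.6.1 flatly contradicts itself, but the text does not establish that. The undefined term is the fault, and the Visit 5 instruction in 7.5 remains too narrow on either reading.

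Third, this is a 30-person, single-dose pilot. Tolerability is assessed by the psycho-behavioral questionnaire on POD 0 and POD 1+1, which the gap does not touch, and no 30-day SAE rate is an endpoint or planned analysis. That limits the consequence. It does not justify stating a window that the schedule does not serve.

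Three stronger inferences are tempting but unsupported:
- **Later events arrive only if someone suspects the drug.** The criterion is participation, which is wider than the drug, and Section 7.5 names routes that need no suspicion.
- **Events before Visit 2 go uncollected.** The look-back inquiry at each visit and the questioning at each contact can recover them. What remains is that the Visit 1 list and Schedule of Events carry no AE entry.
- **Flashbacks or psychotic episodes would be missed as late effects.** Section 1.3 lists them without saying that they occur late, and says side effects typically end 30 minutes after the infusion stops.

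**Conclusion.** The point holds for the period after Visit 5. The plan states a window running to POD 14-16 for non-serious events and POD 37-39 for serious ones, but schedules no contact or record check in its last 7 and 30 days. These are 41-47% and 75-79% of the respective windows counted from POD 0. Events in that time, and unrelated SAEs in particular, have no planned route to the team; they may still surface incidentally.

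This rests on taking Visit 5 as the last study day and on reading the visit lists and Schedule of Events as complete. The number of events that would be missed cannot be estimated from the documents. The primary and secondary efficacy comparisons are unaffected. It should be corrected because following the Visit 5 instruction as written yields incomplete safety data for a window that the protocol says it covers.

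**What to change.** 1. **Instruction and definition.** In Section 7.5, have participants told at Visit 5 to report any event within 7 days, and any serious event or hospital admission within 30 days, whatever the suspected cause. In Section 7.6.1, define the study period so that its relatedness limit applies only after the 7-day and 30-day windows.

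2. **One scheduled check.** Add to Section 6.1.3 and the Schedule of Events, at 30 days after Visit 5 and for all participants, an EPIC chart check plus a REDCap or telephone question. The question should also cover the 7-day non-serious tail. If this is not adopted, state in Section 7.5 and in any report that active assessment ended at Visit 5 and later events were collected passively. Keep the duty to record SAEs that the site learns of.

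3. **Tabulation.** Present AEs by arm using the onset time that Section 7.5 already collects. List pre-infusion events separately, and likewise events in randomized participants who were never infused.

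Cost: items 1 and 3 are wording and programming, with no new data. Item 2 is about 30 short checks using systems the team already has. Asking at day 30 about non-serious events in the first 7 days relies on recall over at least 30 - 7 = 23 days, so those answers will be weaker than the SAE check. Changes to the protocol need IRB approval (Section 13.2).
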